2.7 A conceptual model exists for the specific benefits of an EXS program on brain health in older PLWH compared to HIV(-) individuals. This proposal will mechanistically study the effects of EXS on brain health through indirect and direct pathways⁸¹. We hypothesize that EXS training in older PLWH will primarily affect the indirect pathway by increasing physical fitness (cardiorespiratory capacity and daily physical activity as measured by actigraphy). Observed changes in the indirect pathway will be primarily modulated by decreases in systemic inflammation (hsCRP, IL-6, and D-dimer)^{61, 82, 83} and improved glucose regulation [reduced fasting glucose and improved insulin sensitivity (HOMA-IR)]. We hypothesize that EXS training will also affect the direct pathway, but to a lesser extent, with modest upregulation of growth factors [e.g. brain-derived neurotrophic factor (BDNF), vascular endothelial growth factor (VEGF), and insulin like growth factor (IGF)-1]^{61, 82, 83}. Observed changes in both the direct and indirect pathways will lead to improvements in brain health in older PLWH that can be quantitatively measured by changes in cognition [improved neuropsychological performance (NP) within certain domains (executive, memory, and attention)] and neuroimaging (increases in brain volumetrics and CBF within cortico-striatal networks). While EXS could reduce HAND by these multiple mechanisms (reduced inflammation, improved glucose regulation, increased neurogenesis), the relative strength of these mechanisms remains unknown and is a focus of this proposal.

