6. able to have an MRI
7. able to provide written informed consent
8. all inclusion criteria at PI discretion

Exclusion Criteria

1. approximately >2x/week of moderate (or greater) exercise
2. cardiovascular/cerebrovascular disease or pulmonary disease that precludes ability to safely exercise
3. significant neurological disorders (e.g. stroke, head injury with loss of consciousness for >30 minutes, developmental learning disability)
4. presence of dementia or behavioral disorders that would prevent ability to follow the protocol
5. alcohol or substance abuse/ dependence within the last 6 months (DSM-4 TR)
6. contraindications to MRI scanning (e.g. claustrophobia, pacemaker)
7. pregnant or breast-feeding
8. unable to provide written informed consent
9. currently taking anticoagulants or glucocorticoids
10. all exclusion criteria at PI discretion

2.b Ethical Considerations

All participants will receive an intervention, so no one will be receiving less care than another. Additionally, all participants will receive a free 6-month gym membership if they complete the study.

2.c Subject Recruitment Plans and Consent Process

Drawing on previous experience recruiting and maintaining a large cohort of PLWH at the WUSTL ACTG and ID Clinic, we understand the importance of fostering and maintaining an atmosphere of trust and cooperation among community leaders and agencies serving this group. Accordingly, the WUSTL ACTU and ID Clinic have established and maintained close alliances with HIV healthcare and community organizations. We will continue to draw upon these strong relationships in our recruitment efforts of the 58.3% of all PLWH in the St. Louis area who are \geq 40 years of age. Targeted educational and recruitment in-services will be conducted with both WUSTL and outside community providers to ensure awareness of this project and to assist in identifying eligible participants.

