The resistance exercise training component will follow aerobic exercise and will consist of four upper and three lower body routines (chest press, elbow flexion, latissimus dorsi pull down, triceps press, knee extension, knee flexion, and leg press). A combination of guided-motion machines and free weights will be used. Baseline voluntary maximum strength (1 repetition maximum) will be measured during the first 4 exercise sessions on each exercise station. Resistance training program will initially consist of 1-2 sets of each exercise while lifting a weight that causes muscle fatigue after 8-10 repetitions. A rest period of 2 seconds will be given between repetitions, 1-2 minutes between sets, and 2-4 minutes between each exercise. The trainer will monitor each participant's exercise response, and when the participant can comfortably lift the weight for 12 repetitions on any exercise, the weight (intensity) will be increased (~10%) to cause the muscle group to fatigue after 8 repetitions. This progressive 8-12 repetition cycle is repeated for each exercise over the 26 weeks. Energy expended during resistance exercise will be calculated as weight lifted x number of repetitions completed x distance the weight lifted. Total energy expended over the 26 weeks for the EXS program will be calculated.

SIS: This group will serve as a control group against which to gauge the effects of aerobic and resistance training on cognitive function. Participants in this group will follow the same schedule and format as the EXS group. These participants will also be supervised by the trainer and will receive similar amounts of attention and class interaction as participants in the EXS program. These SIS participants will receive evaluation/instructions on stretching, range of motion, limbering, and toning; but the intensity will be far less than that achieved in the EXS classes. Activities will focus on socialization and flexibility enhancement. As the participant's level of flexibility increases, stretches with increasing levels of difficulty will be incorporated into the program.

At any time, participants may be asked to wear heart rate and blood pressure monitors while in the gym, whether for the SIS or EXS condition. Participants with a history of diabetes may also be asked to do one or more finger sticks at each session to monitor blood sugar levels.

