8. Collection of fasting labs (such as but not limited to CMP, sCRP, CBC w/diff, HbA1C, leptin, D-Dimer, YSI, Insulin/IGF-1/C-peptide/Glucagon, plasma BDNF, plasma VEGF, Adiponectin, IL-6, HOMA-IR/fasting glucose & insulin, glycosylated hemoglobin, plasma IGF-1, soluble CD163, plasma neopterin, galectin 9, etc.) and APOE test (APOE will only be done at baseline, not at follow up). CD4 and VL may also be collected if not available through medical records, and approximately 32 mL of blood will also be taken and banked for future use as documented in the Informed Consent.
9. 3T MRI lasting approximately 1 hour
10. Stool sample and dietary survey.
11. Scheduling of dates/times to attend intervention.

E6 Intervention approximately 3x per week for 26 weeks

1. Subject will be able to make up visits, if missed (i.e. If subject comes in 2x during 1 week, they can come 4x the next week for an average of 3x per week).

E7 1 month stool sample and dietary survey

1. Participants will also be given a stool collection kit and asked to bring samples in at baseline, 1 month, mid-point (approx. 3 months), and final follow-up (approx. 6 months). They will also be asked to complete a dietary survey such as the ASA24 or 24 hour food log each time a stool sample is provided.

E8 Midpoint Assessment

1. Assessments, questionnaires, & other evaluations:

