Principal Stratification (PS) Analysis: An additional exploratory secondary analysis will be done using a Principal Stratification framework 153. This analysis compares the treatment arms separately for four subsets determined by whether participants would adhere to the study on any of the two study arms or not. Accordingly, the four sets are: adherers on both EXS, SIS; non-adherers on both EXS, SIS; adherers on EXS but not on SIS; adherers on SIS but not on EXS. In practice these data are available for only one of the two statuses that the subject is randomized to, but the second status is effectively imputed statistically. This innovative analysis will allow for separate evaluation of effects of EXS intervention for those who can and those who cannot adhere to the exercise plan, and will give insights into the differential effectiveness of the EXS program.

Hypothesis 1b: We will assess if greater improvements in physical function due to an EXS program are associated with better cognitive performance. We will test the mediating effect of improvements in physical function on cognitive performance in two ways: (i) between randomized groups, and (ii) within the EXS group. Linear models will be used to determine the mediating effect of the physical function markers (high/low physical activity and peak VO₂) on the change from baseline in core domain specific Z-scores and the global Z-score, by including these markers, together with group assignment, as predictors in the model. Within the EXS group similar linear models will be fit (without the group variable). Similar analyses for supplemental Z-score domains will be explored in secondary analyses.

Exploratory analyses: A similar analysis will be conducted, (i) including both groups, and (ii) within the EXS group, evaluating the mediating effects of changes in glucose regulation (fasting glucose and HOMA-IR) and chronic inflammation (hsCRP, D-dimer, IL-6) on cognitive endpoints. Other variables to be assessed include neurogenesis factors (BDNF, IGF-1, and VEGF). Additional analyses will control for relevant predictors, using a backward model selection strategy as described above.

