Exploratory analyses: A similar analysis will be conducted, (i) including both groups, and (ii) within the EXS group, evaluating the mediating effects of changes in glucose regulation (fasting glucose and HOMA-IR) and chronic inflammation (hsCRP, D-dimer, IL-6) on neuroimaging endpoints. Other variables that will also be assessed include neurogenesis factors (BDNF, IGF-1, and VEGF). Additional analyses will control

for relevant predictors, using a backward model selection strategy, as mentioned above.

Secondary endpoints: Scores from questionnaires that assess stage of behavior change, social support, self-efficacy, and exercise enjoyment will be incorporated with other quantitative outcome data. Logistic re-gression analyses will be conducted with response variables including: 1) successful complete (Y/N) 2) positive changes in cognitive function (Y/N); 3) positive change in brain structure and function (Y/N). The predictors will be the psychosocial or implementation factor scores. Odds ratios will be computed adjusting for demographic and other characteristics using backward model selection, as discussed before.

Additional Analyses: Baseline characteristics: Baseline demographic, medical, implementation factors, and lab characteristics of participants will be summarized by intervention arm (EXS or SIS) using N (%) for categorical variables, and mean, standard deviation, and range for numeric variables. Between-arms comparisons will use Fisher's exact test (FET) and Wilcoxon rank-sum test (WRST) for categorical and numeric variables, respectively. Neuroimaging comparisons will be adjusted via an analysis of covariance for measures of intra-cranial volume.

Study enrollment and drop-out: The number (%) of participants randomized, N (%) of participants completing 26 weeks, and N (%) of patients lost to follow-up will be summarized overall and by treatment arm, and compared between treatment arms using FET. For participants lost to follow-up we will record dates and reasons (if known) for loss to follow-up. Baseline demographic and medical characteristics will be compared between dropouts and completers using FET and WRST for categorical and numeric variables, respectively.

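### The exploratory HOMA-IR mediation models include everyone, although insulin users are not excluded and HOMA-IR does not measure insulin resistance in them

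*Combined protocol and SAP*

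**What the plan says.** - **Models.** F Statistical Plan, Aim 1, Exploratory analyses, plans models in both arms together and again in EXS alone. Their stated purpose is "evaluating the mediating effects of changes in glucose regulation (fasting glucose and HOMA-IR) and chronic inflammation (hsCRP, D-dimer, IL-6) on cognitive endpoints". The Aim 2 exploratory paragraph repeats this for imaging: "evaluating the mediating effects of changes in glucose regulation (fasting glucose and HOMA-IR) and chronic inflammation (hsCRP, D-dimer, IL-6) on neuroimaging endpoints". Both follow the linear models of Hypotheses 1b and 2b, in which the marker is a predictor of change in the endpoint, together with group or within EXS alone. Neither paragraph restricts by diabetes or drug use.
- **Adjustment.** Further analyses use backward selection of relevant predictors. Neither diabetes nor glucose-lowering treatment is named.
- **The marker.** The fasting labs (E5, item 8, and E10, item 8) list "HOMA-IR/fasting glucose & insulin". B1, section 2.7, treats HOMA-IR as a measure of insulin sensitivity.
- **Who can enrol.** The eligibility lists in D2 2.a and E1 do not exclude diabetes. D3 3.a contemplates it: "Participants with a history of diabetes may also be asked to do one or more finger sticks at each session". The only drug exclusion is "currently taking anticoagulants or glucocorticoids".
- **What is already collected.** C-peptide is in the same fasting labs at baseline and follow-up. A history and physical takes place at both (E5 and E10, item 2). Medication regimens are reviewed at screening (D2 2.c), and medication lists are named as source data (G3). No section asks for changes in glucose-lowering drugs over the 26 weeks to be recorded.

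**The concern.** HOMA-IR is informative because fasting insulin and fasting glucose, taken together, reflect how the participant's own insulin secretion responds to glucose. When insulin is injected, that link is broken: the measured insulin depends at least partly on the drug and on when it was given. The change over 26 weeks then cannot be read as a change in insulin resistance. This follows from how the index is built; the documents do not discuss it.

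Fasting glucose is different. It remains a valid measurement in treated participants, but a change in treatment between the two visits would mix a drug effect with any training effect.

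At stake is the glucose-regulation pathway, which is named in the exploratory hypotheses of both aims (C1). B1, section 2.7, calls the relative strength of the mechanisms a focus of the proposal. If one marker is measured with extra error and the inflammation and growth-factor markers are not, that comparison is tilted against glucose regulation.

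**Working it through.** **1. The plan's own figure.** No power is stated for the mediator models. The nearest figure is the Aim 1 power statement for 80 EXS + 40 SIS completers: d = 0.55 at 80% power. Two-sided 5% is assumed, since the plan gives no level. The noncentral t distribution gives power 0.804 at d = 0.55, and 80% power at d = 0.547. The stated figure reproduces.

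**2. Attenuation of the slope.** Assume:
- a fraction q of participants has a HOMA-IR change unrelated to true insulin resistance and to the endpoint;
- their change has SD r times the SD (s) of the others;
- q and r are the same in both arms, and the mean change is similar.

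The true slope is b. Over everyone analysed:
- covariance of marker and endpoint = (1 − q) × b × s²
- variance of marker = (1 − q) × s² + q × r² × s²

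The estimated slope is therefore b multiplied by

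(1 − q) / [(1 − q) + q × r²]

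| q | r = 1 | r = 3 |
|---|---|---|
| 2% | 0.98 / 1.00 = 0.98 | 0.98 / (0.98 + 0.18) = 0.85 |
| 5% | 0.95 / 1.00 = 0.95 | 0.95 / (0.95 + 0.45) = 0.68 |
| 10% | 0.90 / 1.00 = 0.90 | 0.90 / (0.90 + 0.90) = 0.50 |

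Both q and r are assumptions; the documents give neither. Among 120 completers, 2% is 2.4 people and 10% is 12.

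**3. Direction.** Under these assumptions the noise is unrelated to the endpoint, so it shrinks the slope but should not create an association. A simulation of the planned form (80 + 40, 3,000 runs per setting) with no true association gave false-positive rates of 4.6% to 5.0%, in line with the nominal 5%.

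**4. Cost of leaving insulin users out.** The detectable two-arm d at 80% power serves as a yardstick for lost precision:

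| Left out | Arms | Detectable d |
|---|---|---|
| none | 80 + 40 | 0.547 |
| 2% | 78 + 39 | 0.554 |
| 5% | 76 + 38 | 0.561 |
| 10% | 72 + 36 | 0.577 |

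At 10% the loss is 0.577 / 0.547 = 1.055, or about 5.5%. This agrees with √(120/108) = 1.054.

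**The case against.** - **Insulin is permitted only by silence.** No section says that insulin users will enrol. D3 3.a says only that participants with a history of diabetes may be asked for finger sticks, and D2 2.a leaves the exclusion criteria to the discretion of the principal investigator. This stands as a limit: the number affected is unknown and could be zero. It does not supply a rule for the case where it is not zero.
- **The plan already adjusts for relevant predictors and reviews medications.** This is true, and it would be wrong to say that treatment is ignored altogether. But backward selection keeps a covariate for its association with the outcome and need not keep drug use. Even if kept, it would not turn the HOMA-IR value of an insulin user into a measure of insulin resistance.
- **The analyses are exploratory and HOMA-IR is one of several markers.** The paragraphs name eight: two for glucose regulation, three for inflammation and three growth factors. Only HOMA-IR has the validity problem. This stands, and it limits the weight of the point.

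Two stronger readings are tempting. A reader might infer that session finger sticks would lead to more drug changes in EXS than in SIS. D3 3.a gives monitoring blood sugar as their purpose; no section links the readings to prescribing or suggests a difference between arms. A reader might also infer that insulin users could make the pathway look present when it is not. If their change is noise, the expected result is attenuation, as step 3 of the working shows.

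**Conclusion.** The gap is real but narrow. As written, the plan would use HOMA-IR change as a mediator in any insulin user who enrols, and in that participant the value does not mean what the plan takes it to mean. The likely consequence is an underestimated glucose-regulation pathway in the exploratory analyses of both aims.

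The size cannot be determined from the documents. It runs from nothing, if no insulin user enrols, through a 2% to 10% shrinkage when r = 1, to a halved slope in the most adverse setting shown (q = 10%, r = 3). These figures rest on an assumed share, an assumed SD ratio, and noise unrelated to the endpoint. Hypotheses 1a, 1b and 2a to 2c do not use this marker, so the primary comparisons are untouched. This is an inexpensive improvement to an exploratory analysis and does not threaten the trial's main conclusions.

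**What to change.** In the exploratory paragraphs for Aims 1 and 2 of F Statistical Plan:

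1. Fit the HOMA-IR models only in participants not using insulin at baseline. Because baseline use precedes the intervention, this restriction does not depend on anything that happens under treatment.
2. As a sensitivity analysis, also leave out those who start insulin by week 26. That subset is defined after randomisation, so it should not be the main analysis.
3. Report fasting C-peptide descriptively for insulin users.
4. Record glucose-lowering drugs, and any change in them, at the existing baseline and follow-up history and physical.
5. Repeat the fasting-glucose and HOMA-IR models without participants whose glucose-lowering treatment changed, again as a sensitivity analysis only.

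The cost is a few sentences of SAP text, one data item at two existing visits, and a slightly smaller sample for one exploratory marker. No extra blood draw is needed, and eligibility and clinical management do not change.

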Aim 1: Hypothesis 1a. Primary Analysis of the Study: We will assess if an EXS program in older sedentary PLWH enhances core NP domains (executive function, attention, and memory) compared to a SIS program. The change from baseline to 26 weeks after study intervention for each core domain Z- score and global Z-scores (comprised of the three core cognitive domain Z scores) will be compared between the EXS and SIS groups using t-tests. A 0.5 SD change in global Z-score is considered a clinically meaningful improvement and is currently being used for a pharmacotherapy (maraviroc) trial for HAND 149. In the present trial we anticipate that an EXS program will lead to >0.5 SD change in global Z-scores but we recognize that the precise threshold for individual perception of improvement is variable. For this analysis will use all random-ized subjects, under the intent-to-treat (ITT) paradigm. For participants missing a 26 week endpoint, a value will be imputed based on the lower (worse) half of the distribution from their arm (conservative approach).

Secondary analyses: Mean change in supplementary domain Z-scores at 26 weeks will be compared between the EXS and SIS groups for all randomized participants using the Z-test, under the following scenarios: (a) As treated (AT), with all subjects for whom the endpoint is available included in their allocated group; and (b) Per-protocol (PP), including only adherent participants ($\geq 80\%$ of study visits) for whom the 26 week endpoint is available. Additional multivariable secondary analyses will adjust for demographic and other relevant predictors, including plasma viral load and nadir CD4, gender,

depression, and other potential predictors that are significantly associated with the outcome at the 0.15 level using a backward model selection. In particular, the inclusion of gender and depression will allow for identification of differential changes in NP for men and women, and indirect effects of exercise mediated by depression 150-152. Since this is a medium-size randomized study we expect the unadjusted analysis to yield an unbiased estimate of the treatment effect. The outcomes will be collected only at baseline and follow-up, so a longitudinal analysis using generalized estimating equations or mixed effects models is not necessary as it would yield essentially identical results.

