Aim 2. Hypothesis 2a. Primary Analysis of the Study: We will assess if an EXS program improves brain structure and function more than a SIS program in older sedentary PLWH. Changes in brain volumetrics (hippo-campus, caudate, and anterior cingulate) and regional CBF (hippocampus, caudate, and anterior cingulate) at baseline and 26 weeks will be compared between EXS and SIS groups using a similar design as for Aim 1, including ITT, AT, and PS analyses. The brain imaging outcomes will be adjusted for the relevant markers of brain size. A Holm-Bonferroni correction will be used when evaluating the brain volumetrics across the different regions 154.

Secondary analyses: Similar analyses will also be performed for brain volumetrics and regional CBF in the amygdala, thalamus, and putamen. Additional analyses will control for relevant predictors, using a backward model selection strategy, as mentioned above.

Hypothesis 2b: We will assess if greater improvements in physical function due to EXS are associated with larger brain volumetrics and increases in regional CBF. We will test the mediating effect of improvement of physical function on neuroimaging measures in two ways: (i) between randomized groups, and (ii) within the EXS group. Linear models will be used to determine the mediating effect of the physical function markers (high/low physical activity and peak VO₂) on the change from baseline in structural and functional neuroimaging measures, by including these markers, together with group assignment, as predictors in the model. Within the EXS group similar linear models will be fit (without the group variable).

Hypothesis 2c. We will assess if greater improvements in cognition are associated with improved brain structure and function changes. Linear models will examine the relationship between neurocognitive performance (outcome) and brain structural and functional changes (predictors), using only the 100 participants randomized to the EXS group. These models will adjust for potential confounders, (e.g. plasma viral load and nadir CD4) that are significantly associated with the outcome at the 0.15 level using backward model selection.

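### The secondary implementation-factor models reduce continuous cognitive and imaging change to an undefined Y/N response, losing at least 36% of the information if change is normally distributed

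*Combined protocol and SAP*

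**What the plan says.** Section F, Secondary endpoints, links scores for stage of behaviour change, social support, self-efficacy and exercise enjoyment to outcome by logistic regression. After completion, the listed responses are "positive changes in cognitive function (Y/N); 3) positive change in brain structure and function (Y/N"). On the other side of the model, "The predictors will be the psychosocial or implementation factor scores", and "Odds ratios will be computed adjusting for demographic and other characteristics using backward model selection, as discussed before". Randomized arm is not named as a predictor.

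The same outcomes keep their scale in the rest of section F:

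- Hypothesis 1a: changes in core-domain and global Z-scores "will be compared between the EXS and SIS groups using t-tests".
- Hypothesis 1b: linear models "on the change from baseline in core domain specific Z-scores and the global Z-score".
- Hypothesis 2a: "Changes in brain volumetrics (hippo-campus, caudate, and anterior cingulate) and regional CBF (hippocampus, caudate, and anterior cingulate") are compared between arms with a design like that of Aim 1.
- Hypotheses 2b and 2c: linear models.

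Hypothesis 1a also states that "A 0.5 SD change in global Z-score is considered a clinically meaningful improvement", and adds that "we recognize that the precise threshold for individual perception of improvement is variable". Neither remark is tied to the Y/N responses.

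**The concern.** A yes/no response treats everyone on the same side of the cut as equal, whatever the size of their change. The plan gives no reason for giving up the scale here when it keeps it everywhere else, and the continuous values will already be in the database.

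Two definitions are also missing. The cognitive cut could be zero, 0.5 SD or another value, on the global score or on a domain. The imaging response covers three core regions in two modalities, so six measures, with nothing to say whether one, most or all must improve. Both choices could be made after the data are seen, and they change who counts as a success.

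At stake is the only quantitative model described for asking which participant factors go with cognitive or imaging benefit. The sample is modest and the plan gives no power figure for these regressions.

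**Working it through.** **1. The plan's own power figure.** Inputs are from Power Analysis for Specific Aim 1. Alpha is not stated there; two-sided 0.05 is assumed. With λ = d / √(1/n_EXS + 1/n_SIS), power is approximately Φ(λ − 1.960).

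| n_EXS + n_SIS | d | λ | Normal approximation | Noncentral t |
|---|---|---|---|---|
| 100 + 50 | 0.49 | 2.829 | 0.808 | 0.803 |
| 80 + 40 | 0.55 | 2.840 | 0.811 | 0.804 |
| 60 + 30 | 0.635 | 2.840 | 0.811 | 0.802 |

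The stated 80% reproduces. It concerns the continuous between-arm comparison only.

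**2. Information kept after a cut.** For a normal outcome cut so that a share p falls on one side, efficiency relative to the uncut outcome is φ(c)² / [p(1 − p)], with c = Φ⁻¹(p). It is symmetric in p and largest at p = 0.50. The shares are assumptions, because the documents give none.

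**3. Detectable correlation.** N = 120 completers (80 + 40, from the plan's 20% drop-out). Effective N is 120 × efficiency. With 80% power and two-sided 0.05, r = tanh[(1.960 + 0.842) / √(N_eff − 3)].

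| Response | Efficiency | Loss | Effective N | Detectable r |
|---|---|---|---|---|
| Continuous | 1 | 0% | 120 | 0.25 |
| 50/50 | 0.3989² / 0.25 = 0.637 | 36% | 76 | 0.32 |
| 75/25 | 0.3178² / 0.1875 = 0.539 | 46% | 65 | 0.34 |
| 80/20 | 0.2800² / 0.16 = 0.490 | 51% | 59 | 0.36 |

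The plan does not say which analysis set these models use. With all 150, r would go from 0.23 (continuous) to 0.28 (50/50) or 0.32 (80/20), so the pattern is the same.

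**4. Check by simulation.** One continuous predictor, N = 120, true r = 0.252, 2,000 runs per setting. Power is about 80% for the linear model. For logistic regression it is 60% at a 50/50 split, 55% at about 69/31 and 47% at 80/20.

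**5. How much the missing definitions matter.** Suppose change is normal with no mean shift. A cut at zero labels 50% positive; a cut at 0.5 SD of change labels 31%. With an assumed mean shift of 0.5 SD of change, the shares are 69% and 50%. For the six core imaging measures under no true change, with assumed inter-measure correlation from 0.7 to 0.3, a rule of at least one positive labels about 78-92% as successes. A rule of all six labels about 22% down to 8%.

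**The case against.** The strongest reply is one of scope. These are secondary models without a power claim. The implementation aim rests mainly on questionnaires, focus groups and interviews, and completion, the response closest to scale-up, is truly binary. Responder coding is a common supportive summary. All of that stands, and it makes this a minor point.

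Multiplicity is a fair objection too. Seven continuous responses (global Z, three volumes, three CBF measures) against four scores give 7 × 4 = 28 associations, where two binary responses give 2 × 4 = 8. This is a real but manageable cost in secondary work.

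A reader might infer three stronger things that the documents do not support:

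- **That any gain above zero counts as success.** This is a natural reading of the word positive, but no cut is stated, and the 0.5 SD benchmark in Hypothesis 1a is not excluded. The remark that the threshold varies between individuals is no evidence for a zero cut.
- **That practice effects make most people positive and drive the odds ratios.** Tests are repeated (24 at baseline and follow-up, 15 at midpoint) and no correction is described. But no retest gain is quantified. A gain common to everyone moves the share labelled positive without itself creating an association with psychosocial scores. A gain that varied with those scores would affect a linear model as well. None of this applies to volume or CBF.
- **That a 36-51% loss is a fixed property of the plan.** The range belongs to assumed splits from 50/50 to 80/20 of a normal outcome.

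**Conclusion.** The concern holds for the two dichotomised responses in the secondary implementation-factor models. The plan discards scale it retains for the same outcomes elsewhere, and leaves both the cut and the imaging combination undefined. Under normality the loss is at least 36%, and larger for uneven splits. Over the assumed splits, the detectable correlation rises from 0.25 to 0.32-0.36 with 120 completers. These figures rest on a normal outcome, a single predictor, two-sided 0.05 and the plan's own drop-out assumption.

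It would be wrong to conclude that the trial's main results are weakened. The primary t-tests, the imaging comparison and the linear models for Hypotheses 1b, 2b and 2c use continuous change, and the stated 80% power is unaffected. The point is a cheap gain in precision for a secondary analysis.

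**What to change.** In Secondary endpoints, replace the two change-based logistic models by linear regressions on the psychosocial scores. The responses are change in global Z and, separately, change in volume and in CBF for hippocampus, caudate and anterior cingulate. Include randomized arm and the baseline value of the outcome as covariates in every model, outside the backward selection. Keep logistic regression for completion. If a Y/N version is still wanted, label it supportive and fix in advance its cut-point and the rule for combining regions and modalities.

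The cost is SAP wording; no new data are needed. The odds-ratio summary, which some readers find easier, is lost or becomes supportive. There are more imaging responses. Either extend to them the Holm-Bonferroni correction that Hypothesis 2a already applies to regional volumes, or label the models exploratory.
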